6. STUDY SYNOPSIS

Title	A Prospective, Open label, Non-randomized, Single-Arm, Multicenter Study to Evaluate the Procedural Safety and Efficacy of ELCA [®] in Treatment of Patients with Single or Multivessel Coronary Artery Disease (CAD).
Trial Location	India
Name of the Sponsor	Spectranetics Corporation
Protocol Number	ELCA-1016
Development phase	III
Name of study device	Excimer Laser Coronary Atherectomy (ELCA [®]): Coronary Laser Atherectomy Catheters (OTW and RX) Mode of Application: Invasive Stand-alone modality or in conjunction with Percutaneous Transluminal Coronary Balloon Angioplasty (PTCA)
Indication	Single or Multi vessel Coronary Artery Disease (CAD)
Objective	
Primary Objective: To evaluate the safety and efficacy of ELCA[®] in patients with single or multivessel CAD either as a stand-alone modality or in conjunction with (PTCA),
 
Secondary Objectives:
 
 • To determine post-procedural TIMI Flow grade • Lesion Morphology • Device-related complications • Procedure-related complications
Study Endpoints	
Efficacy Endpoint:
 
 • Device Success: Successful crossing of the Laser Catheter across the entire length of the stenotic lesion • Procedural Success: Target lesions with less than 50% residual stenosis after laser and adjunctive therapy.

Spectranetics Corporation

Study Protocol Number: ELCA-1016

Version 1.0

Dated: 12 Oct 2016

	
Safety Endpoint:
 
 • Freedom from Major Adverse Cardiac Events (MACE) through hospital discharge and at one month. MACE is defined as Death, Non-Q-wave and Q-wave myocardial infarction (MI), Target Lesion Revascularization, Cardiac Tamponade and Life-threatening arrhythmias • TIMI Flow • Lesion Morphology • Device-related complications • Procedure-related complications 	
Device Failure/ Malfunctions	All failures and malfunctions of the study device must be sent to the CRO/Sponsor, preferably within 24 hours of knowledge of the event.	
Study design	Prospective, Open label, Non-randomized, Single-arm, Multicenter study.	
No. of centers	Total 05 sites in India. The center's compliance to the clinical investigation plan will be assessed on an ongoing basis. In case of serious non-compliance, the sponsor may decide to stop patient enrollment in a center based on its assessment.	
Sample Size	30	
Screening & Follow Up	Screening	Day -10 to 0
	Baseline (study procedure)	Day 0
	Clinic follow up visit	30 ± 7 days
	Protocol guided follow-up of patient is vital; Investigators and Site study management team should ensure minimizing follow up lapses and to avoid subjects becoming Lost-To-Follow-Up.	
Study Procedure/ Methodology	Each subject will be followed from enrollment through 30 days ± 7 days for the effectiveness and safety endpoints.	

Spectranetics Corporation

Study Protocol Number: ELCA-1016

Version 1.0

Dated: 12 Oct 2016

	
Upon enrollment after obtaining a written informed consent, each patient will be assigned a unique identification number. Only patients eligible to undergo cardiac catheterizations as per routine practice will be considered for the study. Premedication of patients will be as per the investigator's routine practice. All patient data will be recorded on patient data forms.
 
Screening: This will be performed prior to the cardiac catheterization procedure. Only patients who have consented and fulfill the selection criteria will be enrolled. Additionally, ECG and Echocardiogram will be done using hospital equipment to ensure fulfillment of inclusion/exclusion criteria.
 
Procedure: The entire procedure will be carried out as per the site routine practice and the device will be used as per the IFU.
 
Clinic follow up visit (30 ± 7 days): The subject will return to the clinic at 1 month to evaluate angina status as per the CCS classification, AE assessments, concomitant medications and any coronary intervention that has occurred since the previous contact. An electrocardiogram (ECG) will be repeated during the clinic visit.

Key Inclusion Criteria
	
The subjects have to meet the following inclusion criteria:
 
 • Patient 18 years to 75 years, both inclusive • Have at least one severe stenotic lesion (greater than or equal to 80% diameter stenosis as assessed by visual estimation) • Hemodynamically stable patients coming to the site for cardiac catheterization and angiography who fulfill all the following criteria: 
 ▪ Have no clinically significant cardiac arrhythmias, based on ECG results ▪ Have no evidence of valvular pathology, based on echocardiogram results ▪ Have $\geq 30\%$ left ventricular ejection fraction

Spectranetics Corporation

Study Protocol Number: ELCA-1016

Version 1.0

Dated: 12 Oct 2016

	
(LVEF), based on echocardiogram results.
 
 • Angiographic evidence of calcification or a chronic total occlusion • Vessel reference diameter greater than or equal to 2.0 mm • Patient is willing and able to comply with study requirements • Women of child bearing potential , willing to use at least two methods of contraception

Key Exclusion Criteria
	
The subjects do not meet any of the following exclusion criteria:
 
 • Evidence of acute coronary syndrome within 3 months prior to index procedure • Evidence of acute ischemic events • Cardiogenic and non-cardiogenic shock • Active bleeding or coagulopathy • Previous coronary angioplasty within 6 months of the index procedure • Patients participating in trial for another investigational device/medicine within 1 month prior to enrolment in this study • Acute or Chronic renal failure, Impaired renal function (serum creatinine > 2.5 mg/dl or 221 µmol/l) determined within 72 hours prior to index procedure • Known allergies to the following: Aspirin, Clopidogrel or Ticlopidine, Heparin, Sirolimus or its derivatives, contrast agent (that cannot be adequately pre-medicated), or any metal • Planned surgery within 6 months of enrollment in this study • Life expectancy less than 6 months • Patients known to be suffering from substance abuse

Spectranetics Corporation

Study Protocol Number: ELCA-1016

Version 1.0

Dated: 12 Oct 2016

	
(alcohol or drug)
 
 • Patients with any other significant co-morbid illness which in the opinion of the investigator is not conducive of inclusion in the study. • Known or suspected Pregnancy • Patients not willing to provide written informed consent • In the investigators opinion subjects will not be able to comply with the follow-up requirements.

Data Collection
	
All requested data need to be reported by the centers into an electronic Case Record Form (eCRF).


Statistical analysis
	
As per the 25th SEC (Cardiovascular & Renal) meeting which deliberated the proposals on 30-10-2015 and recommended the firm (Spectranetics Corporation - Sponsor) shall conduct a Bridging study in Indian Population at least 25 patients. The directorate suggested that the sponsor submit a protocol for the study in India for clinical trial approval. Considering the 5 dropouts, Sponsor has set up this protocol to conduct the Excimer Laser Coronary Atherectomy (ELCA[®]) study in India on 30 eligible patients.

Spectranetics Corporation

Study Protocol Number: ELCA-1016

Version 1.0

Dated: 12 Oct 2016

7. LIST OF ABBREVIATIONS

ACC	:	American College Of Cardiology
AE	:	Adverse Event
AHA	:	American Heart Association
AMI	:	Acute Myocardial Infarction
ASADE	:	Anticipated Serious Adverse Device Effect
CABG	:	Coronary Artery Bypass Graft
CAD	:	Coronary Artery Disease
CBC	:	Complete Blood Count
CCS	:	Canadian Cardiovascular Society
CDSCO	:	Central Drugs Standard Control Organization
CFR	:	Code Of Federal Regulations
CIP	:	Clinical Investigational Plan
CK	:	Creatine Kinase
CRO	:	Contract Research Organization
CRF	:	Case Record/Report Form
CRO	:	Clinical Research Orginazation
CV	:	Curriculum Vitae
DCG(I)	:	Drug Controller General Of India
ECG	:	Electrocardiogram
EDC	:	Electronic Data Capture System
ELCA	:	Excimer Laser Coronary Atherectomy
EOT	:	End Of Therapy
FDA	:	Food And Drug Administration
GCP	:	Good Clinical Practice
ICF	:	Informed Consent Form
ICH	:	International Council for Harmonization
IEC	:	Institutional Ethics Committee
IFU	:	Instruction For Use
IHD	:	Ischemic Heart Disease
IRB	:	Institutional Review Board
ISO	:	International Organization Of Standardization
LARS	:	Laser Angioplasty For Restenotic Stents
LVEF	:	Left Ventricular Ejection Fraction
MACE	:	Major Cardiac Adverse Events
mg	:	Milli Gram
MI	:	Myocardial Infarction
mL	:	Milli Litre
OTW	:	Over-The-Wire
PCI	:	Percutaneous Coronary Intervention
PLLA	:	Poly-L-lactic acid
PTCA	:	Percutaneous Transluminal Coronary Balloon Angioplasty

Spectranetics Corporation

Study Protocol Number: ELCA-1016

Version 1.0

Dated: 12 Oct 2016

RX	:	Rapid Exchange
SAE	:	Serious Adverse Event
SAT	:	Sub Acute Thrombosis
SEC	:	Subject Expert Committee
SOP	:	Standard Operating Procedure
SVG	:	Saphenous Vein Bypass Grafts
TIA	:	Transient Ischemic Attack
TIMI	:	Thrombolysis In Myocardial Infarction
TMF	:	Trial Master File
Trop I	:	Troponin I
ULN	:	Upper Limit of Normal
UPT	:	Urine Pregnancy Test
WMA	:	World Medical Association

The following terms will be used synonymously:

- Clinical Investigation Plan (CIP) = Clinical Protocol = Study Plan
- Clinical Investigation = (clinical) Study = (clinical) Trial
- CRF = eCRF
- Study Device = Excimer Laser Coronary Atherectomy (ELCA[®]) Products
- Spectranetics Corporation = Spectranetics = SPNC= Sponsor

Spectranetics Corporation

Study Protocol Number: ELCA-1016

Version 1.0

Dated: 12 Oct 2016

8. STUDY PROCEDURE OVERVIEW

Procedure		Screening (Day -10 to 0)	Coronary Atherectomy	Post Procedure Assessment	30 Days Clinic Follow Up (± 7 Days)	Unscheduled Visit
Informed Consent Signed		X				
Assessment of Eligibility Criteria		X				
Review of Medical History		X				
Review of Concomitant Medications		X	X	X	X	X
Physical Exam	Complete	X				X
	Angina Class (CCS)	X			X	X
	Vital Signs	X		X	X	X
Clinical Laboratory	Chemistry ¹	X ²				
	Cardiac Biomarkers (CK, CK-MB and Trop I)	X ³		X ⁵ , X ⁶		
	Pregnancy Test	X ⁹				
12 Lead Electrocardiogram (ECG)		X ³		X ⁴	X ⁷	X
LVEF measured through the Echo or LV Angiogram		X ²				
Coronary Angiogram		X				X ⁸
Device evaluation by Investigators				X		
Adverse Event Assessment			X	X	X	X

1	Blood chemistry includes Complete Blood Count (CBC) and platelet count, serum sodium, potassium, urea, creatinine, and Random Blood Sugar (RBS)
2	72 hrs prior to the index procedure.
3	24 hours prior to index procedure.
4	24 hours post procedure
5	6 - 24 hours post-procedure or at discharge whichever is earlier.
6	Cardiac Markers: If cardiac biomarkers (CK-MB or Trop I) > 3 time Upper Limit of Normal (ULN) or SAT, CK, CK-MB & Trop I post procedure, the levels must be evaluated every 8 hours until it returns to normal or until hospital discharge.
7	ECG: To be obtained for any suspicious episode of coronary ischemia or SAT during the baseline hospitalization.
8	If angiogram is performed during the unscheduled visit, may be collected.
9	Urine Pregnancy Test to be performed only for women of child bearing potential, within 72 hours before angiography

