12.5 STUDY ENDPOINTS

Efficacy Endpoint:

- Device Success: Successful crossing of the ELCA Catheter across the entire length of the stenotic lesion
- Procedural Success: Target lesions with less than 50% residual stenosis after laser and adjunctive therapy

Safety Endpoint:

- Freedom from major adverse cardiac events (MACE) through hospital discharge and at one month
MACE is defined as Death, Non-Q-wave and Q-wave myocardial infarction (MI), Target Lesion Revascularization, Cardiac Tamponade and Life-threatening arrhythmias
- TIMI Flow
- Lesion Morphology
- Device-related complications
- Procedure-related complications

In order to fully characterize the procedure, information of all treated lesions will be collected irrespective of whether the lesion has been treated with ELCA[®] product.

Electronic Case Report Forms will be utilized to collect relevant information.

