13.9 POST PROCEDURE ASSESSMENT (UNTIL DISCHARGE)

The index procedure will be considered as complete, when the guiding catheter has been removed from the subject and the subject has left the cardiac catheterization laboratory. If a guiding catheter is reinserted thereafter, it will be considered as a re-intervention. Relevant CRF will be completed for such re-intervention. Following post procedure parameters will be assessed after the Coronary Atherectomy:

1. Vital Signs

Subject's vitals will be assessed immediately post PCI as per the Investigator's discretion.

2. Laboratory Evaluation

Cardiac biomarkers (CK, CK-MB and Trop I) will be performed 06-24 hours / or at discharge of post-procedure whichever is earlier. If the cardiac biomarkers (CK-MB or Trop I) are 3 times above the upper limit of normal or in case of Sub Acute Thrombosis (SAT), CK, CK-MB & Trop I must be evaluated every 8 hours until it returns to normal or until hospital discharge.

3. Electrocardiogram

12-lead electrocardiogram will be obtained 24 hours post procedure. Electrocardiograms should also be obtained for any episodes suspicious for coronary ischemia or SAT during the baseline hospitalization.

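### For a subject discharged before 6 hours, the only unconditional post-procedure cardiac-marker sample may fall before the protocol's own 6-24 hour window, so a silent non-Q-wave MI could go uncounted in MACE

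*Protocol*

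**What the plan says.** - **Marker timing.** Section 8, footnote 5, puts the post-procedure marker sample at "6 - 24 hours post-procedure or at discharge whichever is earlier". Section 13.9 repeats the rule: the markers "will be performed 06-24 hours / or at discharge of post-procedure whichever is earlier".
- **Repeat sampling.** Section 8, footnote 6, and section 13.9 call for further samples only if CK-MB or troponin I exceeds three times the upper limit of normal, or on subacute thrombosis. In that case "the levels must be evaluated every 8 hours until it returns to normal or until hospital discharge".
- **Other marker samples.** The row "Cardiac Biomarkers (CK, CK-MB and Trop I") in the section 8 table is marked at screening and post-procedure only. It has no entry at the 30-day visit.
- **ECG.** Section 13.9, whose heading covers the period up to discharge, also says: "12-lead electrocardiogram will be obtained 24 hours post procedure".
- **Endpoint.** Section 12.5 lists freedom from MACE, through hospital discharge and at one month, as the first safety endpoint: "MACE is defined as Death, Non-Q-wave and Q-wave myocardial infarction (MI), Target Lesion Revascularization, Cardiac Tamponade and Life-threatening arrhythmias". No marker or ECG criterion for MI is given.
- **Length of stay.** No minimum stay is stated.

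**The concern.** The window opens at 6 hours, but its discharge limb has no lower bound. For a subject who goes home at, say, 4 hours, discharge is the earlier event and the sample is taken then, outside the window that the protocol itself sets. If that value is low, nothing triggers another marker sample, and none is scheduled later.

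A non-Q-wave MI without symptoms would be found mainly through these markers. A missed MI leaves the MACE-free rate unchanged if the subject has another MACE event, and otherwise raises it. The error therefore runs in one direction, in the device's favour. In a single-arm study of 30 subjects there is no control group in which the same loss would occur, and one event is visible in the result. No later analysis can recover blood that was not drawn.

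**Working it through.** **1. The plan's own figure.** Section 15 sets a minimum of 25 patients plus 5 dropouts: 25 + 5 = 30. This reproduces and is not in dispute. The protocol states no expected MACE rate or performance goal.

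**2. The marker rule by time of discharge.**

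| Discharge | When the rule places the sample | Inside 6-24 h? |
|---|---|---|
| Before 6 h | At discharge | No |
| 6 to 24 h | By discharge | Yes, if drawn at or after 6 h |
| After 24 h | 6-24 h | Yes |

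Only the first row is a problem.

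**3. The ECG rule beside it.** If every subject stayed at least 24 hours, the discharge limb of the marker rule would never apply. The marker rule thus contemplates discharge before 24 hours. The ECG rule in the same section is set at 24 hours and does not say what happens then. The two are unreconciled.

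**4. Effect of one missed MI** (in a subject with no other MACE event):

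- N = 30: 1/30 = 3.3 points. N = 25: 1/25 = 4.0 points.
- At N = 30, 30/30 = 100% (exact 95% CI 88.4 to 100) if the MI is missed, and 29/30 = 96.7% (82.8 to 99.9) if it is counted.

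**5. Possible average size.** None of the three inputs is in the documents. They are assumptions:

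- r = rate of marker-only MI, 3 to 10%
- f = share of subjects sampled before 6 h, 10 to 50%
- m = chance that an early sample misses the MI, 50 to 100%

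Expected overstatement = r × f × m. Chance of at least one missed MI in 30 subjects = 1 − (1 − r × f × m)^30.

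| Case | r × f × m | Overstatement | Chance of ≥ 1 missed |
|---|---|---|---|
| Low | 0.03 × 0.10 × 0.50 = 0.0015 | 0.15 points | 4.4% |
| Middle | 0.05 × 0.25 × 0.50 = 0.00625 | 0.6 points | 17.1% |
| High | 0.10 × 0.50 × 1.00 = 0.05 | 5.0 points | 78.5% |
| No discharge before 6 h | f = 0 | 0 | 0 |

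The high case needs half of all subjects to leave before 6 hours, which fits poorly with a 24-hour ECG.

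**6. What counting both ways would show.** If k subjects have only a sample before 6 h and no recorded MACE event, the two counts differ by k/30. For k = 1 the gap is 3.3 points. For k = 3 it is 10.0 points: 30/30 = 100% against 27/30 = 90.0% (exact 95% CI 73.5 to 97.9).

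**The case against.** The strongest reply is that discharge before 6 hours may hardly occur. The 24-hour ECG, the eight-hourly repeats and the references to a baseline hospitalization all suggest a longer stay, and the subjects have severe stenosis with calcification or a chronic total occlusion. The discharge limb can also be read as a backstop, so that nobody leaves without a sample; removing it with no return draw would turn early samples into missing ones. Even a missed event is small beside an exact interval about 17 points wide at 29/30, and no stated decision rule would change. All this stands. It limits the size of the problem, but it does not change what the rule permits.

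Four stronger readings are tempting, and the documents do not support them:

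- **The marker and ECG rules contradict each other for every discharge before 24 hours.** They do not. A subject discharged between 6 and 24 hours can be sampled inside the window, and the ECG can be done on return or logged as a deviation.
- **An early low value ends all detection of MI.** It ends scheduled marker sampling only. The 24-hour ECG, ECGs for suspected ischemia, the 30-day angina and adverse-event review, and unscheduled visits can still reveal an MI.
- **An early low value is recorded as no MI.** The protocol does not say so. Classification may be set in a statistical analysis plan that is not at hand, and its absence here is no fault. With no MI criterion stated, the link from marker to MI is itself an inference, though a reasonable one for non-Q-wave MI.
- **The bias differs by site because sites follow routine practice.** Sections 6 and 13.8 use that phrase of the procedure, not of discharge.

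**Conclusion.** The point holds in a narrow form. As written, the rule lets the one unconditional post-procedure marker sample fall before 6 hours in a subject discharged that early, and no scheduled marker sample would correct this. What is exposed is a clinically silent, marker-only non-Q-wave MI in such a subject, and any miss can only raise the MACE-free rate or leave it unchanged.

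The size cannot be fixed from the documents. One missed MI is worth 3.3 points at N = 30. The average overstatement is 0.15 to 5.0 points over the assumed ranges, and zero if nobody leaves before 6 hours. The 24-hour ECG suggests that such discharges would be few, so the effect is probably small. It merits a change because the change is cheap and the lost information cannot be recovered afterwards.

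**What to change.** - **Reconcile the timings.** Bring section 8 footnote 5, section 13.9 and the 24-hour ECG into agreement, so that the marker sample used for the endpoint is consistent with the 6-24 hour window that the protocol states. This needs no discharge rule, and none is proposed here.
- **Record the time** of the end of the procedure, of each marker sample and of discharge, so that early samples can be identified.
- **Report freedom from MACE both ways:** once with subjects whose only post-procedure sample was drawn before 6 hours counted as MI-free, and once with them counted as having had an MI. If there are none, the two figures coincide and one line says so.

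The cost is about one sentence in each of two places, the time fields on the case report form and one extra table row. The downside is that a few early-discharged subjects may need a later draw, or be treated as not evaluable for marker-based MI.

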9. BACKGROUND AND INTRODUCTION

Ischemic Heart Disease (IHD) has been recognized as a leading cause of death globally. According to the most recent health statistics, WHO's Global Health Statistics 2008, coronary artery disease (CAD) will be the number one *killer* in 2030, causing 14.2% of all deaths worldwide. Acute coronary syndrome (ACS) is an acute clinical presentation of CAD; it refers to a range of acute myocardial ischemic states.^{2,3} It encompasses unstable angina, non-ST segment elevation myocardial infarction (ST segment elevation generally absent), and ST segment elevation myocardial infarction (persistent ST segment elevation usually present).

Since its inception in 1977, balloon angioplasty has undergone major improvements but has persistent shortcomings in the form of abrupt closure and restenosis. Balloon angioplasty has lower success rates in management of long lesions, calcified vessels, bifurcation lesions, saphenous vein graft stenosis and ostial narrowings. It is possible that some of these angiographic characteristics, which have been identified as relatively complex by American College of Cardiology /American Heart Association (ACC/AHA) task force may be handled more effectively by a procedure that removes atherosclerotic plaque such as excimer laser coronary angioplasty. Studies have reported that excimer laser – facilitated coronary angioplasty, in contrast to balloon angioplasty is equally successful in treating simple and complex lesions.⁴

Atherectomy is a procedure which is performed to remove atherosclerotic plaque from diseased coronary and peripheral arterial vasculature. Atherectomy devices are designed to cut, shave, sand or vaporize these plaques and have different indications.

Various available techniques for atherectomy are:

1. Directional atherectomy where the direction can be adjusted, which is useful for eccentric lesions,
2. Rotational atherectomy where the burr spins concentrically and is mostly used in calcified coronaries,
3. Orbital atherectomy where the crown orbits the wire and is used in both coronary and peripheral arterial disease and,
4. Excimer Laser atherectomy which ablates the tissue and is used in both coronary and peripheral arterial disease.

When excimer laser irradiation is used in the setting of PTCA, the major advantage of this technique is thought to be ablation of the atherosclerotic plaque with minimal thermal and mechanical injury

to the adjacent vessel wall structures⁹.

As opposed to the mandatory fissuring and cracking of the plaque and over distending the arterial wall using conventional coronary angioplasty¹⁰, laser atherectomy might have the theoretical potential of reducing complications and probably as a result of reduced injury, of decreasing the incidence of restenosis.

LASER is an acronym for Light Amplification by Stimulated Emission of Radiation. Although the history of laser begins in 1951, the first medical application is reported by Goldman in 1962 and used in 1963 for the experimental ablation of atherosclerotic plaques. The first clinical applications were performed by Choy and Ginsburg in 1983.

[figure not shown]

Figure 1: ELCA[®] Mode of Action

Spectranetics Corporation

Study Protocol Number: ELCA-1016

Version 1.0

Dated: 12 Oct 2016

Excimer Laser Coronary Atherectomy (ELCA[®]) uses the high energy, monochromatic light beam to alter or dissolve (vaporize) the plaque without damaging the surrounding tissue. Fiber-optic catheters are used to deliver this light beam. For endovascular applications, Xenon Chloride excimer laser is used and its fiber-optic catheter has multiple small fibers, rather than just a few large fibers, in order to be flexible enough to navigate in the arterial tree.

Laser can be used in both coronary and peripheral applications. In coronaries, excimer laser can be used to remove thrombi; to vaporize pro coagulant reactants in addition to debulking the underlying plaque; and to facilitate stent delivery. In the CARMEL multicenter study, excimer laser angioplasty was successfully used in more than 90% of the enrolled 151 acute myocardial infarction (AMI) patients with a large thrombus burden with a relatively low rate (8.6%) of major cardiac adverse events (MACE). It has been also used for in-stent restenosis: in the Laser Angioplasty for Restenotic Stents multicenter registry (LARS), laser angioplasty reduced 30-day repeat-target-site coronary intervention, but it did not decrease in 1 year. Balloon-resistant lesions, chronic total occlusions, calcified lesions, and under expanded stents in calcified lesions are some other scenarios in which excimer laser coronary atherectomy can be successfully used.

The original excimer laser coronary angioplasty (ELCA) devices Model numbers PC1014 and PC1017, known as the “Soft Rim” versions were originally submitted to the FDA through the PMA approval process in 1991 Submission P910001. The devices were indicated for use in patients with single or multivessel coronary artery disease either as a stand-alone treatment or in conjunction with percutaneous transluminal coronary angioplasty (PTCA) and in patients who are acceptable candidates for coronary artery bypass graft (CABG) disease. These models obtained approval from the FDA for use in 1993. CE mark was granted in 1996.

